11.1 Sample size calculation

The primary endpoint is the number of diagnoses of Ng plus Ct over the study period (12 months) whilst individuals are screened vs. not screened.

Numerators: Cumulative number of diagnoses of Ng plus Ct in 12 months in screening/non-screening arms. Each participant can only contribute one diagnosis of Ct and one diagnosis of Ng per (scheduled or unscheduled) visit - regardless of number of sites infected. Thus each participant can contribute up to 2 diagnoses (Ct/Ng) at each (scheduled or unscheduled) visit. The numerator includes laboratory-confirmed diagnoses made between scheduled visits, performed inside or outside of the study.

Denominators: Number of scheduled study visits with available results for the diagnosis of Ng/Ct. The denominator does not include unscheduled visits.

Testing for these infections is performed at each three-monthly visit, i.e. 4 follow-up visits per subject (if complete follow up). Ng/Ct are tested for at 3 sites at each visit – rectum/pharynx and urethra. If a participant is found to be infected with one of these infections at more than one site on a particular visit this is counted as a single infection. If they are found to have both Ng and Ct at a visit this is classified as 2 infections.

Based on the Be-PrEP-ared study from ITM, we assume at baseline visit 79% have 0 diagnoses (pre treatment), 18% have 1 diagnosis (either NG or CT) and 3% has 2 diagnoses (both NG and CT). With screening, the number of diagnoses in the Follow Up (FU) visits depends on number of diagnosis at baseline and is shown below.

	0 diagnoses [#]	1 diagnosis [#]	2 diagnoses [#]	Average nr of diagnoses
0 diagnoses at baseline	86%	13%	1%	0.15
1 diagnosis at baseline	76%	20%	4%	0.28
2 diagnoses at baseline	71%	24%	5%	0.34

[#]These columns refer to the percentage of participants who have 0/1/2 diagnoses at each follow-up visit. In other words, of those with 0 diagnoses at baseline (first row), at each of the visits at 3,6,9 and 12 months, 86% will have 0 diagnoses, 13% will have 1 diagnosis and 1% will have 2 diagnoses.

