Over 4 FU visits, this yields an average of 0.72 diagnoses per subject. Using a Poisson regression model with $\log(\text{number of visits})$ as offset, the 95% confidence interval of the log ratio (no screening vs. screening) is calculated. The 'no screening' arm is considered to be non-inferior if there is an increase of maximal 25% in number of diagnoses (i.e. increase of an average of 0.72 to 0.90 per 4 visits). The 'no screening' arm is proven to be non-inferior if the upper limit of the 95% confidence interval is lower than $\log(1.25)$. The required sample size to detect non-inferiority of the 'no screening' arm is calculated by simulation, assuming no difference between arms.

Assuming that 95% of the participants will have data on all 4 visits, and 5% will have data on only 3 visits, the required sample size to obtain 80% power is 912. Assuming an additional 10% drop out rate we will need to enroll 1014 participants.

The current number of PrEP participants at the ITM/HSP/EH/CHU/UZG is 803/739/290/260/240, respectively. At all 5 centres this number is increasing by approximately 20% per year. 99.7% of these individuals are MSM and over the age of 18. We estimate that 80% of the 2332 PrEP participants in these five centres will agree to participate. This number (n=1866) exceeds the number we need to enroll in the study (n=1014). By the commencement of the study (begin 2020) we estimate we will have 1518/886/464/314/298 individuals in the PrEP cohorts at the ITM/HSP/EH/CHU/UZG whom we will be able to screen for participation.

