11.3.2 Primary outcome analysis

We will analyse the primary outcome both using Intention-to-Treat and Per-Protocol approaches, with Per-Protocol as primary approach. In the Intention-to-Treat analysis, all participants will be analysed according to their randomized allocation, even in case they receive another intervention, show protocol violations prior to or during the study, or are lost-to follow. In the per-protocol analysis only participants who receive intervention as planned, and follow the protocol as planned

are included. If the person urgently requires knowing if they are infected with Ng/Ct or not this will be done by repeat testing for these infections. If this test is positive for Ng/Ct then this will be counted as an intervisit infection in the final analysis. In each arm, the incidence of Ng plus Ct will be estimated together with 95% confidence interval. Estimates will be based on a Poisson regression model with number of diagnoses as dependent variable, arm as independent variable, log(number of visits) as offset and a random intercept for site. This model will also provide an estimate of the log incidence rate ratio (no screening versus screening), together with 95% confidence interval. The 'no screening' arm is proven to be non-inferior if the upper limit of the 95% confidence interval is lower than log(1.25).

Visits with missing data on the diagnosis of Ng or Ct, will be excluded from the calculation of the incidence rate (excluded both from numerator and denominator).

Subgroup analysis:

We will conduct a prespecified sensitivity analysis to assess the incidence of Ng plus Ct in screening vs. non-screening arms ***in participants with lower-risk behavior***. An individual with lower-risk behavior is defined a priori as those individuals who report 4 or fewer partners per 3-month period in all 5 relevant 3 month periods. These periods are the 3-months prior to study enrollment as well as the four 3 month periods during study follow up). The analysis will be analogous to the analysis of the primary objective, but restricted to participants with lower-risk behavior.

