Interim analyses are planned at two time points: once 50% and 100% of all study recruits have passed their 6 month visit. For the first interim analysis, data is used of the first 507 enrolled participants (i.e. ordered by randomization date) until 6 months follow-up. For the second analysis, data is used of all enrolled participants until 6 months follow-up. The goal of the interim analyses (at both time points) is to estimate the incidence rate ratio of symptomatic Ng plus CT. Estimates will be based on a Poisson regression model (or a negative binomial regression model if there is overdispersion) with number of symptomatic diagnoses as dependent variable, arm and hospital as independent variables and log(number of visits) as offset. This model will provide estimates of the incidence rate in each arm and the incidence rate ratio (no screening versus screening), together with 95% confidence interval. Visits with missing data on the diagnosis of Ng or Ct, will be excluded from the calculation of the incidence rate (excluded both from numerator and denominator).

7. Analysis of main efficacy outcomes: Incidence of Ng plus Ct

In each arm, the incidence of Ng plus Ct will be estimated together with 95% confidence interval. Estimates will be based on a Poisson regression model (or a negative binomial regression model if there is overdispersion) with number of diagnoses as dependent variable, arm and hospital as independent variables, and log(number of visits) as offset. This model will also provide an estimate of the log incidence rate ratio (no screening versus screening), together with 95% confidence interval. The 'no screening' arm is proven to be non-inferior if the upper limit of the 95% confidence interval is lower than $\log(1.25)$.

Visits with missing data on the diagnosis of Ng or Ct, will be excluded from the calculation of the incidence rate (excluded both from numerator and denominator).

In a sensitivity analysis, the numerator of the primary endpoint will only include diagnoses if there was a negative test result at the prior visit.

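### The stated 80% power at 912 allows for almost no correlation between a participant's follow-up visits; with an interval that allows for overdispersion it is between about 67% and 79%, depending on a correlation the documents do not give

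*Protocol*

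**What the plan says.** Protocol section 11.1 sets the planning inputs. For baseline, "we assume at baseline visit 79% have 0 diagnoses (pre treatment), 18% have 1 diagnosis (either NG or CT) and 3% has 2 diagnoses". A table then gives the follow-up distribution for each baseline group, and its footnote applies the same percentages throughout: for those with no diagnosis at baseline, "at each of the visits at 3,6,9 and 12 months, 86% will have 0 diagnoses, 13% will have 1 diagnosis". The margin is an "increase of an average of 0.72 to 0.90 per 4 visits". No screening is "proven to be non-inferior if the upper limit of the 95% confidence interval is lower than" log(1.25). Sample size was found by simulation with a Poisson model, "assuming no difference between arms", with 95% of participants having four visits and 5% having three. The result is that "the required sample size to obtain 80% power is 912", raised to 1014 for 10% dropout.

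The section does not say how a participant's four visits were generated, how strongly they correlate, or which standard error was used.

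The analysis model differs between the documents. Protocol section 11.3.2 uses Poisson regression with "log(number of visits) as offset and a random intercept for site", and has no term for the participant. SAP section 7 names Poisson, "or a negative binomial regression model if there is overdispersion) with number of diagnoses as dependent variable", with hospital as a covariate. It gives no test or threshold for overdispersion, and the SAP does not revisit power.

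**The concern.** Each participant contributes a count summed over up to four visits. If some participants are persistently at higher risk than others, that count varies more than a Poisson variable, and an honest confidence interval is wider than the Poisson one.

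The planning table shows persistence of this kind. Baseline status shifts the expected count at every follow-up visit by the same amount, month 12 included. A scheme with visits independent given baseline would nevertheless make month 9 a much weaker predictor of month 12 than month 0 is. That requires one baseline test to capture nearly all lasting differences in risk.

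Two things are at stake. With a valid interval, the chance of an inconclusive result when the arms are equal may exceed the 1 in 5 that the sponsor has accepted. If the interval is not widened, the chance of wrongly declaring non-inferiority exceeds 2.5%. Protocol sections 2 and 11.4 would use a non-inferior result to recommend stopping Ng/Ct screening.

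**Working it through.** **Inputs (Protocol 11.1).** Baseline 0/1/2 diagnoses: 79/18/3%. Follow-up means per visit by baseline group: 0.15, 0.28, 0.34. Margin 1.25, true ratio 1, two-sided 95% interval. 456 per arm, mean visits 0.95×4 + 0.05×3 = 3.95.

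**1. Mean and events.** 0.79×0.15 + 0.18×0.28 + 0.03×0.34 = 0.1791 per visit, or 0.7164 over four visits (the protocol's 0.72). Events per arm: 456 × 0.7164 × 3.95/4 = 322.6. Poisson SE of the log ratio: √(2/322.6) = 0.0787.

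**2. Variance per visit.** The within-group variances are 0.1475, 0.2816 and 0.3244.
- Weighted within-group: 0.1769.
- Between-group: 0.79×0.15² + 0.18×0.28² + 0.03×0.34² − 0.1791² = 0.0033.
- Total: 0.1802.

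**3. Reproducing the plan.** If visits are independent given baseline, the dispersion φ (variance/mean of the four-visit count) is (4×0.1769 + 16×0.0033)/0.7164 = 1.06. The correlation between follow-up visits is 0.0033/0.1802 = 0.018. Power with the Poisson SE is Φ[(log 1.25 − 1.96×0.0787)/(0.0787×√1.06)] = 80.2%; 2,000 simulated trials gave 80.8%. Dropout: 912/0.9 = 1014 after rounding up.

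**4. Correlation with baseline in the same table.** Baseline mean 0.24, variance 0.2424. Covariance: 0.18×1×0.28 + 0.03×2×0.34 − 0.24×0.1791 = 0.0278. Correlation: 0.0278/√(0.2424×0.1802) = 0.133, the same for months 3, 6, 9 and 12. This is about seven times 0.018.

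**5. Dispersion if follow-up visits share that correlation (assumption).**
- Equal correlation r = 0.133: φ = 0.1802×(1 + 3×0.133)/0.1791 = 1.41.
- Covariance scaled to the lower follow-up mean (0.0278×0.1791/0.24 = 0.0208): φ = (4×0.1802 + 12×0.0208)/0.7164 = 1.35.
- Half the correlation, r = 0.0665: φ = 1.21.

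**6. Results at 912.** Power with a dispersion-corrected interval is Φ[log 1.25/(0.0787√φ) − 1.96]. One-sided error of plain Poisson at ratio 1.25 is 1 − Φ(1.96/√φ).

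| Follow-up correlation | φ | Power, corrected interval | Error of plain Poisson |
|---|---|---|---|
| 0.018 (independent given baseline) | 1.06 | 78.6% | 2.9% |
| half of 0.133 | 1.21 | 73% | 3.7% |
| as with baseline, scaled covariance | 1.35 | 68.3% | 4.6% |
| as with baseline, equal correlation | 1.41 | 66.6% | 4.9% |

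**7. Simulation of the SAP rule.** This used 2,000 trials per setting, with negative binomial whenever Pearson dispersion exceeded 1 and the hospital term omitted. Power was 79.9% under conditional independence, and 67.5% and 66.7% at φ of 1.38 and 1.42. Monte Carlo error is about 1 percentage point, so the first result cannot be told apart from 80%.

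**The case against.** The strongest reply is that nothing in section 11.1 is miscalculated. On a natural reading of its assumptions 80% is right, and the lower figures come from a different assumption. That stands: this is a question about a power assumption, not an arithmetic error.

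A reader might go further and infer that the protocol's own table implies dispersion of 1.3–1.4, so that power on the plan's own inputs is about two thirds. The documents do not support this. The table gives follow-up distributions conditional on baseline and says nothing about how follow-up visits relate to one another. The identical percentages at months 3 to 12 may be a pooled simplification. Baseline is also a different state: it is pre-treatment, with mean 0.24 against 0.179, and the follow-up figures apply under screening.

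Nor can the simulation scheme be treated as known. A pure Poisson count would give 80.9%, and an ordinary number of replicates would hardly separate that from 80.2%.

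The SAP's negative binomial option also answers much of the error-rate concern. With about 900 participants, dispersion of 1.3–1.4 should be evident and the switch would be made. What remains is that the trigger is undefined and that the protocol's model has no such option.

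Finally, section 11.1 includes laboratory-confirmed diagnoses between scheduled visits in the endpoint, yet the calculation adds no events for them. They could offset part of the loss; the documents do not allow the amount to be worked out.

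**Conclusion.** The concern holds as a gap in the power assumption. The stated 80% belongs to a Poisson analysis with almost no within-person correlation, whereas the SAP allows for overdispersion and power was not restated.

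Analytically, no reading of the table with a dispersion-corrected interval reaches 80% at 912 on the scheduled-visit event rate. At the favourable end the shortfall is trivial (78.6% by formula, 79.9% by simulation). If follow-up visits correlate with each other as they do with baseline, power is 67–68%, so an inconclusive result with equal arms has a chance of about 1 in 3. The lasting association with baseline makes some correlation above 0.018 plausible, but its size is not in the documents, and 67–68% should not be read as the plan's true power.

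The error-rate figures of 2.9% to 4.9% apply only if plain Poisson is kept. Under the SAP's alternative the main risk is an inconclusive trial, not a false claim. This should be fixed; confidence in the size of the shortfall is moderate.

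**What to change.** **Protocol 11.1.** Re-run the simulation with the SAP's analysis model and an explicit participant-level correlation, estimated from the source PrEP cohort if visit-level data are available. State the correlation assumed, how visits were generated and which standard error was used. Replace the unqualified 80% with the resulting figure, or with a range if the correlation cannot be estimated. Say whether diagnoses between visits are counted.

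**Protocol 11.3.2 and SAP 7.** Name one primary method that is valid under within-person clustering and drop the condition on overdispersion. Negative binomial regression, or Poisson with robust participant-level standard errors, would serve. Use the same model in both documents.

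**Cost.** One simulation and some rewording. The stated power will probably look less favourable, and intervals will be slightly wider than plain Poisson intervals. No extra enrolment or data collection is asked for.

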11.2 Planned recruitment rate

The 5 centres will begin recruitment at the same time and will continue recruiting all PrEP participants until the recruitment target is reached (estimated 8-month recruitment period). The planned recruitment rate will be 127 individuals per month for this 8-month period. To the best of our knowledge, there are no other trials being conducted currently or planned that are evaluating the same research question or a version thereof.

11.3 Statistical analysis plan

11.3.1 Summary of baseline data and flow of participants

Participants in each intervention group, and in each site, will be described with respect to baseline characteristics. The description will be in terms of medians/means and quartiles/standard deviations for continuous characteristics and using counts and percentages for categorical characteristics. The clinical importance of any imbalance will be noted though statistical tests of significance will not be undertaken.

Details of participants screened, those who meet the study inclusion criteria, those who are eligible and randomized, those who are eligible but not randomized, those who withdraw from the study after randomization and those who are lost to follow-up will be summarized in a CONSORT flow diagram. The number (%) of participants attending scheduled follow-up visits will be reported.

11.3.2 Primary outcome analysis

We will analyse the primary outcome both using Intention-to-Treat and Per-Protocol approaches, with Per-Protocol as primary approach. In the Intention-to-Treat analysis, all participants will be analysed according to their randomized allocation, even in case they receive another intervention, show protocol violations prior to or during the study, or are lost-to follow. In the per-protocol analysis only participants who receive intervention as planned, and follow the protocol as planned

are included. If the person urgently requires knowing if they are infected with Ng/Ct or not this will be done by repeat testing for these infections. If this test is positive for Ng/Ct then this will be counted as an intervisit infection in the final analysis. In each arm, the incidence of Ng plus Ct will be estimated together with 95% confidence interval. Estimates will be based on a Poisson regression model with number of diagnoses as dependent variable, arm as independent variable, log(number of visits) as offset and a random intercept for site. This model will also provide an estimate of the log incidence rate ratio (no screening versus screening), together with 95% confidence interval. The 'no screening' arm is proven to be non-inferior if the upper limit of the 95% confidence interval is lower than log(1.25).

Visits with missing data on the diagnosis of Ng or Ct, will be excluded from the calculation of the incidence rate (excluded both from numerator and denominator).

Subgroup analysis:

We will conduct a prespecified sensitivity analysis to assess the incidence of Ng plus Ct in screening vs. non-screening arms ***in participants with lower-risk behavior***. An individual with lower-risk behavior is defined a priori as those individuals who report 4 or fewer partners per 3-month period in all 5 relevant 3 month periods. These periods are the 3-months prior to study enrollment as well as the four 3 month periods during study follow up). The analysis will be analogous to the analysis of the primary objective, but restricted to participants with lower-risk behavior.

11.3.3 Secondary outcome analysis

- 1) We will compare the antimicrobial exposure (ceftriaxone/azithromycin/doxycycline) in the two arms. Antimicrobial exposure will be measured as number of standard doses per 1000 person-years based on standard WHO and ECDC methodology [41]. Data on all antimicrobials consumed will be collected at each study visit and will include antimicrobials consumed at other health facilities such as at participant's General Practitioner. A Poisson regression model with number of standard doses as dependent variable, arm as independent variable, log(time at risk) as offset and a random intercept for site will be fitted.
- 2) Incidence rate of symptomatic Ng and Ct. This information will be collected at all visits and will include episodes of symptomatic Ng and Ct diagnosed elsewhere as long as these were laboratory confirmed diagnoses – either based on molecular testing or in the case of Ng, culture. The analysis will be analogous to the analysis of the primary objective, but the endpoint is calculated using symptomatic infections only.
- 3) Incidence rate of syphilis. The European IUSTI case definition of a syphilis infection will be followed [51]. A Poisson regression model with number of incident syphilis infections as dependent variable, arm as independent variable, log(time at risk) as offset and a random intercept for site will be fitted.
- 4) Incidence rate of HIV. A Poisson regression model with incident HIV infection as dependent variable, arm as independent variable, log(time at risk) as offset and a random intercept for site will be fitted.
- 5) Economic impact of cessation of 3x3 screening in MSM in Belgium (see section 11.4)
- 6) Participants' perception/experience and preference for screening vs. no screening (see section 8.11, only for ITM subjects)

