4.3 Endpoints

4.3.1 Primary endpoint

Incidence of Ng plus Ct detected at any site whilst individuals are screened vs. not screened.

Numerators: Cumulative number of diagnoses of Ng plus Ct in 12 months in screening/non-screening arms. Each participant can only contribute one diagnosis of Ct and one diagnosis of Ng per (scheduled or unscheduled) visit - regardless of number of sites infected. Thus each participant can contribute up to 2 diagnoses (Ct/Ng) at each (scheduled or unscheduled) visit. The numerator includes laboratory-confirmed diagnoses made between scheduled visits, performed inside or outside of the study.

Denominators: Number of scheduled study visits with available results for the diagnosis of Ng/Ct. The denominator does not include unscheduled visits^a.

The diagnosis of Ng and Ct will be made via nucleic acid amplification testing (NAAT) performed on rectal and pharyngeal swabs and urine.

In the primary analysis, the primary endpoint (as described above) includes all Ng/Ct diagnoses. Hence it is implicitly assumed that every diagnosis is a new infection. It is however possible that an Ng/Ct infection detected at the 3 to 12 month visit in the non-screening arm is simply a non-resolved infection from the prior visit (see Figure 5)^b. This could spuriously increase the measured incidence in the non-screening group. Because

^a The rationale for this definition of the denominator is to, as closely as possible, reflect time at risk of testing Ng/Ct positive. If an individual misses one of their 4 study follow up visits then this reduces their probability of being diagnosed with Ng or Ct by one quarter (assuming no other relevant variables change). Our denominator definition takes this into account by only including study visits where we have results of Ng/Ct testing. Unscheduled visits are not included as these make up a very small proportion of all visits and could be considered to bias the time at risk estimate.

[figure not shown]
^b Given the natural rate of clearance of Ng and Ct from each site, this probability is very low

this risk only applies to the non-screening arm it results in a bias towards exaggerating the effect of screening on incidence. As such if our study finds that non-screening is non-inferior to screening this finding could not be explained by this bias. In a sensitivity analysis, the numerator of the primary endpoint will only include diagnoses if there was a negative test result at the prior visit.

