If a patient has evidence of clinical treatment failure this is a separate issue and we instruct patients to return for further tests if they have persistence of their symptoms. This is also not considered a new infection and will thus not be included in the primary or secondary outcomes as new infections.

All the following investigations are optional for any unscheduled visit:

- Ask if symptoms compatible with STI
- Physical examination
- STIs diagnosed since last visit (at study site or outside)
- Antibiotic usage
- Collection of results of syphilis and HIV testing (performed according to routine practice)
- Sample collection:
 - o Urine sample (first-void) (Ng/Ct NAAT)
 - o Pharyngeal swab (Ng/Ct NAAT)
 - o Anorectal swab (Ng/Ct NAAT)
 - o Pharyngeal or anorectal swab for every site that was Ng NAAT positive (Ng culture)

As is the case for routine PrEP visits currently, at every visit (scheduled or unscheduled) there will be some time for STI counselling and discussions of any concerns of the participants related to the study or not.

Assessing and confirming if a study participant has had a Ct/Ng infection in between study visits.

At the month 3, 6, 9 and 12 visits, the participants will be asked if they have had any symptoms of an STI since their last visit or if they have been tested for an STI since their last visit. If the answer to either of these questions is 'yes', then the study team will proceed with the Ng/Ct diagnosis verification protocol.

1. Obtain further information as to what the symptoms were, if any, and what anatomical sites were tested
2. Find out at which health provider (e.g. general practitioner (GP)) was the diagnosis made
3. Establish what antimicrobial therapy was received
4. Laboratory confirmation will be obtained of test results. The following will be regarded as laboratory proof of a Ct/Ng diagnosis:
 - a. The participant has documented proof of a diagnosis of Ng/Ct based on a laboratory report.
 - b. Laboratory evidence of a positive Ng/Ct diagnosis based on NAAT or Ng culture that can be obtained by the study team via: (1) online laboratory reporting systems

such as COZO, (2) telephonic contact with the laboratory or (3) telephonic contact with the health provider who performed the test.

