5.2. Efficacy study endpoints

Primary endpoint

Incidence of Ng plus Ct detected at any site.

Numerators: Cumulative number of laboratory-confirmed diagnoses of Ng plus Ct in 12 months in screening/non-screening arms. Each participant can only contribute one diagnosis of Ct and one diagnosis of Ng per (scheduled or unscheduled) visit - regardless of number of sites infected. Thus each participant can contribute up to 2 diagnoses (Ct/Ng) at each (scheduled or unscheduled) visit. The numerator includes laboratory-confirmed diagnoses made between scheduled visits, performed inside or outside of the study.

Denominators: Number of scheduled study visits with available results for the diagnosis of Ng/Ct. The denominator does not include unscheduled visits.

The diagnosis of Ng and Ct will be made via nucleic acid amplification testing (NAAT) performed on rectal and pharyngeal swabs and urine.

If the person urgently requires knowing if they are infected with Ng/Ct or not this will be done by repeat testing for these infections. If this test is positive for Ng/Ct then this will be counted as an intervisit infection in the final analysis.

In the primary analysis, the primary endpoint (as described above) includes all Ng/Ct diagnoses. Hence it is implicitly assumed that every diagnosis is a new infection. It is however possible that an Ng/Ct infection detected at the 3 to 12 month visit in the non-screening arm is simply a non-resolved infection from the prior visit. This could spuriously increase the measured incidence in the non-screening group. Because this risk only applies to the non-screening arm it results in a bias towards exaggerating the effect of screening on incidence. As such if our study finds that non-screening is non-inferior to screening this finding could not be explained by this bias. In a sensitivity analysis, the numerator of the primary endpoint will only include diagnoses if there was a negative test result at the prior visit.

Because any positive Ng/Ct test from the test of cure visits is considered a non-resolved old infection, these will not be included in the primary or secondary outcomes as new infections. If however the test of cure was to assess if an Ng infection had cleared and a new Ct infection was detected at the test of cure visit then this would be included as a new infection in the primary and secondary study outcomes.

Secondary endpoints

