7.2. Other aspects

a. *Multiplicity*

As this is a study with a single primary efficacy endpoint, no multiplicity adjustments are needed.

b. *Missing data*

Visits with missing data on the diagnosis of Ng or Ct, will be excluded from the calculation of the incidence rate (excluded both from numerator and denominator).

8. Analysis of secondary objectives

8.1. To compare the antimicrobial exposure (ceftriaxone/azithromycin/doxycycline) in the screening and non-screening arms

A Poisson regression model (or a negative binomial regression model if there is overdispersion) with number of standard doses as dependent variable, arm and hospital as independent variables and log(time at risk) as offset will be fitted. Time at risk will be calculated from day of enrollment until end of follow-up.

8.2. To assess if not screening MSM on PrEP for Ng/Ct is non-inferior compared to screening in terms of the incidence rate of symptomatic Ng and Ct infections

In each arm, the incidence of symptomatic Ng plus Ct will be estimated together with 95% confidence interval. Estimates will be based on a Poisson regression model (or a negative binomial regression model if there is overdispersion) with number of symptomatic diagnoses as dependent variable, arm and hospital as independent variables and log(number of visits) as offset. This model will also provide an estimate of the log incidence rate ratio (no screening versus screening), together with 95% confidence interval. The 'no screening' arm is proven to be non-inferior if the upper limit of the 95% confidence interval is lower than log(1.25).

Visits with missing data on the diagnosis of Ng or Ct, will be excluded from the calculation of the incidence rate (excluded both from numerator and denominator).

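### Symptomatic Ng/Ct is scaled by scheduled visits with a result although episodes are counted over all follow-up, so the ratio shifts if attendance or result availability differs by arm

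*Protocol*

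**What the plan says.** Protocol 11.3.3 item 2 carries the primary model over to symptomatic infections: "The analysis will be analogous to the analysis of the primary objective, but the endpoint is calculated using symptomatic infections only". SAP 8.2 spells the model out, "with number of symptomatic diagnoses as dependent variable, arm and hospital as independent variables and log(number of visits) as offset", and tests non-inferiority against the same 1.25 margin. SAP section 6 uses the same offset for the two interim looks at symptomatic Ng/Ct, with data up to 6 months.

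SAP 5.2 defines the denominator as "Number of scheduled study visits with available results for the diagnosis of Ng/Ct. The denominator does not include unscheduled visits". On the numerator it says: "The numerator includes laboratory-confirmed diagnoses made between scheduled visits, performed inside or outside of the study". For the symptomatic endpoint, protocol 11.3.3 adds that the information "will include episodes of symptomatic Ng and Ct diagnosed elsewhere as long as these were laboratory confirmed diagnoses".

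The reason for counting visits is in footnote a of protocol 4.3.1: if a participant "misses one of their 4 study follow up visits then this reduces their probability of being diagnosed with Ng or Ct by one quarter", the denominator should shrink with it.

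Protocol 8.7 encourages participants to come in at any time with symptoms. At each follow-up visit "the participants will be asked if they have had any symptoms of an STI since their last visit", or been tested since then.

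Antimicrobial exposure, syphilis and HIV use log(time at risk) in both documents (protocol 11.3.3; SAP 8.1, 8.3 and 8.4).

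**The concern.** Footnote a's reasoning suits infections found by scheduled sampling, where no visit means no swab and no detection. It fits symptomatic infection less well. A man with symptoms can be diagnosed at an unscheduled visit or by another provider, and his next attended visit looks back over the whole gap. If he misses month 6 but attends months 3, 9 and 12, his between-visit episodes over 12 months can all be counted, against an exposure of three visits.

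Two further rules act in the same direction:

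- SAP section 3 turns an out-of-window scheduled visit into an unscheduled one. It leaves the denominator, while its positive results can still count.
- A visit without a result is dropped from numerator and denominator, but the rule does not remove episodes diagnosed between visits.

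Protocol 10.1.1 names an increase in symptomatic Ng/Ct in the no-screening arm among the study's largest safety concerns. The same outcome informs the DSMB's two-fold criterion. The estimate should therefore not depend on how many scheduled visits happened to yield a result.

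**Working it through.** **Inputs from the documents.** Four scheduled follow-up visits, of which two fall by month 6. Planned attendance is 95% of participants with 4 visits and 5% with 3 (protocol 11.1). The per-protocol population needs at least three scheduled visits with a result (SAP 5.1.2, Table 1).

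**The plan's own figures.** Mean diagnoses per visit = 0.79 × 0.15 + 0.18 × 0.28 + 0.03 × 0.34 = 0.1791, or 0.716 over four visits (stated 0.72). Mean visits = 0.95 × 4 + 0.05 × 3 = 3.95. The Wald formula gives n per arm = 2(1.96 + 0.84)² / (ln(1.25)² × 0.1791 × 3.95) ≈ 446, total 892. Simulating the plan's model at 912 gives 80.2% power, and 912/0.90 rounds up to 1014. The sample size reproduces and is not affected by this point.

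**Formula.** Let m be the share of scheduled visits without a counted result, in men who remain in follow-up. Let f be the share of symptomatic diagnoses that only the scheduled visit would have caught. The documents do not give f, so it is varied from 0 to 1. Relative to a person-time rate, the per-visit rate is multiplied by

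(1 − f·m) / (1 − m).

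**One man.**

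| Situation | f = 0 | f = 0.5 | f = 1 |
|---|---|---|---|
| 1 of 4 visits not counted (m = 0.25) | 1/0.75 = 1.33 | 0.875/0.75 = 1.17 | 1.00 |
| 1 of 2 visits not counted, interim (m = 0.5) | 1/0.5 = 2.00 | 0.75/0.5 = 1.50 | 1.00 |

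**Whole trial at planned attendance.** With f = 0 the rate is multiplied by 4/3.95 = 1.013. The factor is the same in both arms, so it cancels from the ratio.

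**Unequal attendance (assumed figures).** Suppose 95% of visits count with screening and 90% without.

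- f = 0: 0.95/0.90 = 1.056.
- f = 0.5: (0.95/0.90) / (0.975/0.95) = 1.0556/1.0263 = 1.03.
- Reversed, f = 0: 0.90/0.95 = 0.947, which favours non-inferiority.

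**What such a gap requires.** In the per-protocol population a man can lack at most one visit, so if a share p lacks one, the proportion of visits counted is 1 − p/4. Figures of 95% and 90% mean p = 20% and 40%. The plan expects 5%.

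**Early withdrawal.** Data are used up to withdrawal (protocol 8.12.1), so visits and time fall together and there is little bias.

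**The case against.** The case against is mainly about size, and much of it stands.

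- At planned attendance the effect is 1.3% on the rate and nothing on the ratio. Protocol 11.3.4 reports high adherence, tied to collecting PrEP prescriptions every three months, and section 3 promises the same follow-up intensity in both arms.
- Footnote a's rationale does not fail altogether. Scheduled visits ask about symptoms, examine symptomatic men and take samples, so some symptomatic infections are diagnosed there. That is why the range over f is needed.
- Attendance at scheduled visits will be reported (protocol 11.3.1, SAP 4.1), so poor attendance would be visible, although a split by arm is not explicit.

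Three stronger readings are tempting, and the documents do not support them.

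- *The shift could use up half the margin.* With 95% versus 85% of visits the multiplier is 0.95/0.85 = 1.118, and ln 1.118 = 0.111 against ln 1.25 = 0.223. In the per-protocol population this needs 20% of one arm and 60% of the other to lack a visit, and it also takes f = 0.
- *The protocol expects unequal attendance.* Table 3 in protocol 11.4 lists regular attendance of higher-risk men as a benefit of screening. It describes screening as a policy, in a section on an economic analysis placed outside the trial. If it did operate, the no-screening arm would attend less, which raises the ratio and works against non-inferiority.
- *The no-screening arm will have no results at the interim looks.* Protocol section 5 and SAP 2.1 say that samples from that arm are processed or reported only at the end of the study. The wording leaves open which, so missing interim results cannot be concluded from it.

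What remains is that nothing in the plan guarantees equal attendance or result availability. The trial is unblinded, and no reason is given for treating this outcome differently from the other time-based ones.

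**Conclusion.** The mismatch between numerator and denominator is in the text and is worth correcting, but its expected effect is small. An individual rate is overstated by up to 33% for one of four visits and by up to a factor of 2 for one of two at the interim. Both are upper limits that assume no symptomatic diagnosis depends on the scheduled visit.

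The ratio between arms moves only if attendance or result availability differs by arm among men still in follow-up, and it can then move in either direction. An assumed gap of five percentage points in visits shifts it by at most about 6%. The documents give no reason to expect a particular gap. This is a moderate point on a secondary endpoint that carries safety weight. It does not touch the primary analysis or the sample size.

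**What to change.** In protocol 11.3.3 item 2, SAP 8.2 and SAP section 6:

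- Use log(time at risk) as the offset for symptomatic Ng/Ct. Run it from enrolment to the last visit or contact at which symptomatic episodes were ascertained, capped at the month-12 visit, or at month 6 for the interim looks. The end date needs stating: SAP 8.1 says only end of follow-up, and protocol 8.12.3 settles loss to follow-up at study closure, so time without ascertainment could otherwise enter the denominator.
- For this endpoint, do not exclude visits for lack of a scheduled Ng/Ct result.
- Keep the visit-based offset as a sensitivity analysis.
- Report person-time and the number of visits with results by arm.

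The cost is a small wording change and one offset, since time at risk is already derived for three other secondary outcomes. The downside is some dilution of the rate where a symptomatic infection would have been found only at a visit that was missed. The retained sensitivity analysis shows how much the choice of offset matters.
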